Assessment of current AETs	X					X	X	X	X	X	X	X
Medical/surgical history	X											
Seizure History ^d	X											
Concomitant medications	X	X	X	X	X	X	X	X	X	X	X	X
Vital Signs ^e	X	X	X	X	X	X	X	X	X	X		
Clinical Labs	X		X	X		X	X	X	X	X		
Physical Exam	X											
Height/Weight	X		X	X	X	X	X	X	X	X		
Head Circumference	X					X			X	X		

	SCREENING PERIOD	INITIAL TREATMENT PERIOD					EXTENDED TREATMENT PERIOD				Taper Period	Follow-up Period
Visit	1	2	3	4	5	6	7	8	9	Early Withdrawal ^m	6 days	30 days
Day	-14 to -1	Titration Days 1	Titration Day 4	Day 7	Day 14 ^a	Day 15 EOS ^b (+ 5 days)	Week 6	Week 10	Week 13 EOS ^b			
Neurological Exam ^f	X	X	X	X	X	X	X	X	X	X		
Study Drug Dosing		X ^g	X ^h	X ^h	X ^h	X ⁱ	X ⁱ	X ⁱ	X ⁱ	X ⁱ	X ^j	
Assess AEs		X	X	X	X	X	X	X	X	X	X	X
PK blood sampling ^k						X						
Investigator CGI-S	X											
Investigator CGI-I						X				X		
Seizure Diary ^l	X	X	X	X	X	X	X	X	X	X	X	
Meal Diary ⁿ					X	X						

Abbreviations: AE = adverse event; AETs = antiepileptic therapies; CGI-I = Clinical Global Impression-Global Improvement Scale; CGI-S = Clinical Global Impression-Severity; EEG = electroencephalography; EOS = End of Study; ICF = informed consent form; PK = pharmacokinetic.

^a Patients will be admitted to the study center as an inpatient on Day 14 and discharged on Day 15 following the completion of End of Study assessments.

^b End of Study assessments will be completed at Day 15 for partial and non-responder patients and Week 13 for patients who complete the extension period of the study.

^c Patients will have a minimum of a 9-hour video EEG that includes at least one full sleep-wake cycle during their Screening Visit and a 24-hour video EEG at Visit 5 (Day 14 to Day 15) during the Initial Treatment Period. A minimum of 9-hour video-EEG will be performed during the Extended Treatment Period to

confirm parent/caregiver report of relapse or complete resolution or at Early Withdrawal for patients who have continued into the Extended Treatment Period. A Video EEG is not required for patients who decide to withdraw during the Initial Treatment Period

^d To assess preliminary efficacy, a seizure history will be collected at screening to record the approximate number of seizures in the last 28 days as reported by the parent/caregiver.

^e Vital signs will be taken after approximately 5 minutes seated or supine, depending on patient ability. On Day 1 (Visit 2), vital signs should be taken predose and at 4 hours postdose. On all other days, the assessment will be completed predose.

^f A brief neurological examination will be performed, except for the Screening Visit, Visit 6, Visit 9 and Early Withdrawal which will be a complete neurological exam. On Day 4 (Visit 3), and Day 7 (Visit 4) a brief neurological examination will be performed predose and approximately 2 hours following administration of the morning dose of the investigational product. Additional examinations may be performed at the discretion of the investigator.

^g On Day 1 (Visit 2), patients will receive the initial titration dose of vigabatrin (50 mg/kg/day divided twice daily [BID]), and either CBD 20 mg/kg/day plus matching CBD 20 mg/kg/day placebo or CBD 40 mg/kg/day placebo, each drug administered twice daily for three days.

^h For those patients who tolerate the initial dose, the dose for vigabatrin will be increased to 100 mg/kg/day [BID], and either CBD 30 mg/kg/day plus matching CBD 10 mg/kg/day, or CBD 40 mg/kg/day placebo for 3 days. On Day 7 (Visit 4) the dose of vigabatrin will be increased to 150 mg/kg/day and CBD to 40 mg/kg/day for the remaining 9 days for subjects who tolerate the previous dose.

ⁱ Complete Responders will continue receiving their assigned treatments of vigabatrin plus either CBD 40 mg/kg/day or matching placebo for 75 days, until Week 13 (Day 90) to monitor treatment response. During the extended treatment period the Investigator can only down titrate once to 30 mg/kg/day.

^j All subjects will be tapered off vigabatrin as follows: 150 mg/kg/day will be reduced to 100 mg/kg/day for 3 days then the 100 mg/kg/day will be reduced to 50 mg/kg/day for 3 days and then discontinued. Similarly, all subjects will be tapered off CBD or CBD Placebo according to the following schedule: 40 mg/kg/day will be reduced to 30 mg/kg/day for 3 days, then 30 mg/kg/day will be reduced to 20 mg/kg/day for 3 days, then discontinued. Patients will receive a follow-up phone call 4 weeks after completing the tapering. Drug reconciliation will be completed at the end of study.

^k A blood sample for PK analysis will be obtained on Day 15 prior to the second dose during the 24-hour video EEG.

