1.3.3. Selected Clinical Safety Data

Insys study [INS011-14-029](#) enrolled 62 patients with refractory seizures between 1 and 17 years of age. Cannabidiol Oral Solution, 300 mg/mL at doses between 10 mg/kg/day and 40 mg/kg/day were generally well tolerated and no patient discontinued. Fifty-two of the 61 patients enrolled into a long-term safety study ([INS011-14-030](#)). Study INS011-14-030 was a long-term, open-label, 48-week study for pediatric patients aged 1 year to 17 years with refractory epilepsy who participated in the Phase 1/2 Study INS011-14-029.

Insys recently completed a long-term safety study (INS011-14-030) in pediatric patients with refractory epilepsy who participated in the Phase 1/2 PK study (INS011-14-029). This study was a long-term, open-label, 48-week study for pediatric subjects aged 1 year to 17 years with refractory epilepsy who participated in the Phase 1/2 Study INS011-14-029. A total of 52 subjects (9 infants, 26 children, and 17 adolescents) were enrolled and received at least one dose of the investigational product in this study. Forty-five (86.5%) subjects completed the study including follow-up. Seven (13.5%) subjects prematurely discontinued treatment and study participation: 2 (3.8%) subjects due to AEs, 3 (5.8%) subjects due to withdrawal of consent, 1 (1.9%) subject due to death considered not related to investigational product, and 1 (1.9%) subject due to other reason (reported lack of efficacy).

The mean modal dose (defined as the dose with the longest duration) was 24.42 mg/kg/day and the mean total duration of study drug was 311.1 days. Overall, 13 subjects (14.4%) had dose reductions during the study: 12 subjects (13.3%) had dose reductions due to an AE and 1 subject (1.1%) had a dose reduction due to “other” reason. The incidence of dose reductions resulting from an AE was higher for subjects who received 40 mg/kg/day (8 subjects, 30.8%) compared with subjects who received 20-<30 mg/kg/day (6 subjects, 8.8%) and 30-<40 mg/kg/day (1 subject, 6.6%). No subjects who received 10-<20 mg/kg/day and no infants had dose reductions. The trend was to increase the doses over the course of the study. There were 39 subjects (43.3%) who had dose increases during the study. The incidence of dose increases was higher for subjects who received 10-<20 mg/kg/day (14 subjects, 100%) compared with subjects who received 20-<30 mg/kg/day (16 subjects, 47.1%) and 30-<40 mg/kg/day (9 subjects, 56.3%).

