3.1.1. Initial Treatment Period

- Day 1 (Visit 2): Patients will receive the initial titration dose of vigabatrin (50 mg/kg/day divided twice daily [BID]), and either CBD 20 mg/kg/day plus matching CBD 20 mg/kg/day placebo or CBD 40 mg/kg/day placebo, each drug administered BID for 3 days.
- Day 4 (Visit 3): Patients will return to the study center to evaluate medical status (seizure diary, vital signs, and neurological exam), clinical laboratory assessments, concomitant medications, height/weight, and assess adverse events (AEs). For those patients who tolerate the initial dose, the dose for vigabatrin will be increased to 100 mg/kg/day BID, and either CBD 30 mg/kg/day and matching CBD placebo 10 mg/kg/day, or matching CBD 40 mg/kg/day BID placebo for 3 days.
- Day 7 (Visit 4): Patients will return to the study center to evaluate medical status (seizure diary, vital signs, and neurological exam), clinical laboratory assessments, concomitant medications, height/weight, and assess AEs. For those patients who tolerate the increased doses, the dose of vigabatrin will be increased to 150 mg/kg/day and CBD or CBD placebo to 40 mg/kg/day for the remaining 9 days. Vigabatrin, CBD, and matching placebo will be administered in a twice daily fashion at 12-hour intervals with meals.

As part of their standard of care, investigators will assess safety and tolerability of the treatment regimens throughout the study period. All subjects will continue on their treatment until confirmation from the central reader on the 24-hour video EEG and clinical laboratory results are received.

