3.4. Dose Adjustment Criteria

During the Extended Treatment Period, the investigator may reduce the dose of CBD or CBD placebo once from 40 mg/kg/day to 30 mg/kg/day for safety or tolerability. In addition, tapering of vigabatrin and CBD will be required as described in [Section 3.1.4](#).

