4.1.2. Extended Treatment Period

Following the Initial Treatment Period:

- Complete Responders will continue receiving their assigned treatments of vigabatrin plus either CBD 40 mg/kg/day or placebo for 75 days, until Week 13 (Day 90), to monitor progress for treatment response.
- During the Extended Treatment Period, the investigator may reduce the dose of CBD or CBD placebo to 30 mg/kg/day for safety or tolerability. If the subjects cannot tolerate the 30 mg/kg/day, the drug will be discontinued and the patient withdrawn from the study following the completion of the Taper Period.

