### **11.3. Total Duration of Therapy, Average Daily Dose, Maximum Daily Dose, Final Daily Dose of Study Medication, and Compliance**

Exposure to study medication in days will be presented for the Safety Population, by treatment category and overall. Patients are expected to complete the study drug as prescribed, however, if safety or tolerability issues arise the patient will be counted as a treatment failure and discontinued. The following parameters will be summarized by assigned treatment group:

- Total duration of study medication at any dose
- Number and percent of patients who received their full randomized dose for the duration of the study
- Compliance with prescribed dosing (Number and percent of patients who had at least one dose modification, changed, interrupted, or permanently discontinued)

Interruptions, compliance, and dose changes are not included in the calculation of duration of exposure. Total duration of study medication is defined as the number of days between date of first study medication administration to date of last study medication administration + 1.

The corresponding listing will present first/last dose dates, does the subject complete the treatment duration, reason for end of treatment and duration of exposure (days).

In addition, dose modifications will be summarized by treatment and overall in terms of:

- Number of subjects with at least one dose modification (as defined [Section 14.1](#))
- Number of subjects with at least one dose changed
- Number of subjects with at least one dose interrupted
- Number of subjects with dose permanently discontinued
- Number of subjects per reason of dose modification
  - o Adverse event
  - o Lack of efficacy
  - o PK-analysis result
  - o Other

A patient who experiences several dose modifications for the same reason will be counted only once for this reason. A patient who experiences several dose modifications due to different reasons will be counted once for each reason.

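### SAP 11.3 counts tolerability cases as treatment failures who discontinued, although the protocol permits one CBD reduction; a dropped word in footnote h and an outdated SAP regimen also need correcting

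*Protocol*

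**What the plan says.** **Tolerability.** Protocol 3.4 provides, for the extension only: "the investigator may reduce the dose of CBD or CBD placebo once from 40 mg/kg/day to 30 mg/kg/day for safety or tolerability". Footnote i of the Schedule of Events agrees: "During the extended treatment period the Investigator can only down titrate once to 30 mg/kg/day". The next step is in protocol 4.1.2, and 3.1.2 has the same rule: "If the subjects cannot tolerate the 30 mg/kg/day, the drug will be discontinued and the patient withdrawn from the study". SAP 11.3 has a different rule, with no period attached: "if safety or tolerability issues arise the patient will be counted as a treatment failure and discontinued". The same SAP section then lists, among the dose-modification summaries, "Number of subjects with at least one dose changed".

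**Day 4 dose.** Footnote h of the Schedule of Events gives the step as "either CBD 30 mg/kg/day plus matching CBD 10 mg/kg/day, or CBD 40 mg/kg/day placebo for 3 days". Protocol 3.1.1 gives it as "either CBD 30 mg/kg/day and matching CBD placebo 10 mg/kg/day, or matching CBD 40 mg/kg/day BID placebo for 3 days".

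**Regimen.** SAP section 1 says that the SAP rests on protocol V2.0 of 30 October 2017. Its dosing text (Technical Summary Report and section 3.1) takes CBD from 20 to 40 and vigabatrin from 50 to 100 mg/kg/day on Day 4, with no later step. The supplied protocol steps CBD through 20, 30 and 40 and vigabatrin through 50, 100 and 150 mg/kg/day. Its reference list cites posters from a meeting in December 2017, so it is the later document.

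**The concern.** Tolerability is a secondary objective (protocol 2.2). It will be judged largely from descriptive tables of who stayed on drug, at what dose, and why others stopped. The SAP rule makes any safety or tolerability problem end in discontinuation, whereas the protocol keeps the infant on blinded treatment at a lower dose. A programmer who applied the SAP sentence would class continuing infants as having stopped, which overstates tolerability failure and contradicts the dose-change count beside it.

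Footnote h is a smaller matter, but it sits in the table that sites use as a working reference for dosing infants. The older SAP regimen matters because 11.3 counts patients who received their full randomized dose and summarizes compliance with prescribed dosing. Both need the current prescription as the yardstick.

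**Working it through.** **1. One case under each rule.** Take a Complete Responder who has an adverse event at Week 6, is lowered from 40 to 30 mg/kg/day, and stays to Day 90.

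| Source | Status of this infant |
|---|---|
| Protocol 3.4, 3.1.2, 4.1.2, footnote i | Permitted reduction; continues in the study |
| SAP 11.3, rule in the text | Treatment failure, discontinued |
| SAP 11.3, dose-modification list | Dose changed, reason adverse event; not permanently discontinued |

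The second row conflicts with the other two. SAP 11.3 refers to section 14.1 for the definition of a dose modification, but 14.1 is a sample list of data listings and defines nothing.

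**2. How many infants.** Under the response rates assumed in protocol 8.2, the expected Complete Responders, and so the infants to whom a reduction could apply, are:
- CBD arm: 0.60 × 130 = 78
- placebo arm: 0.40 × 60 = 24

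A reduction rate for these infants is not available.
- Protocol 1.3.3 and 4.4 report no dose reductions among infants in the sponsor's earlier studies. The long-term study had 9 infants, not all at 40 mg/kg/day. Zero of 9 has a one-sided 95% upper limit of 1 − 0.05^(1/9) = 28%, so it does not show that the rate is near zero.
- The all-ages figure in 1.3.3 is "The incidence of dose reductions resulting from an AE was higher for subjects who received 40 mg/kg/day (8 subjects, 30.8" per cent). It covers 48 weeks, whereas this extension lasts 75 days. Its counts do not reconcile: reductions for adverse events by dose sum to 8 + 6 + 1 = 15, but the text gives 12 subjects; and 13 subjects at 14.4% implies 13/0.144 ≈ 90 patients, whereas 52 enrolled.
- The documents give no rate for placebo.

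**3. Footnote h.** Read literally, active CBD on Days 4 to 6 would be 30 + 10 = 40 mg/kg/day, or 3 × 40 = 120 against the intended 3 × 30 = 90 mg/kg. Four places make the 10 mg/kg/day component placebo: the synopsis and sections 3.1.1, 4.1.1 and 7.2.1.3. Footnote g keeps the word in its parallel Day 1 sentence. Footnote h itself then raises CBD to 40 on Day 7, which would be no increase on the literal reading.

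**4. SAP regimen against the protocol.**

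| Item | Protocol | SAP |
|---|---|---|
| CBD, Days 1–14, mg/kg | 3×20 + 3×30 + 8×40 = 470 | 3×20 + 11×40 = 500 |
| Vigabatrin, Days 1–14, mg/kg | 3×50 + 3×100 + 8×150 = 1,650 | 3×50 + 11×100 = 1,250 |
| Initial + extended period, days | 15 + 75 = 90 | 14 + 76 = 90 (section 3.1); 14 + 63 = 77 (section 4, nine weeks) |
| Who enters the extension | Complete Responders | Complete and Partial Responders |
| Taper | 6 days | 3 days |
| Primary EEG | Day 14 to 15 | Day 13 to 14 |

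**The case against.** The best defence is that the SAP sentence has no output behind it. The discontinuation reasons in SAP section 8, the parameters in 11.3 and the planned tables in 14.2 contain no treatment-failure category, so a reduced infant would probably be tabulated as a dose change. The sentence also suits the Initial Treatment Period, where the protocol allows no reduction and 3.3 lists intolerable side effects among the grounds for stopping. It may simply be left over from V2.0, which cannot be seen here. SAP section 1 expects revision for amendments before database lock.

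Much of this stands, and it limits the harm. It does not remove the contradiction: the sentence is not confined to the initial period, and 11.3 gives no way to choose between its two rules.

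Three stronger readings are tempting, but the documents do not support them.
- **That infants will receive 40 mg/kg/day of active CBD on Days 4 to 6.** The intended dose is explicit in four other places, and kits are prepared blinded from the randomization schedule (protocol 4.2, 4.3).
- **That up to 0.308 × 78 ≈ 24 CBD-arm infants would be misclassified.** That rests on the all-ages rate whose counts do not reconcile.
- **That the 11.3 rule alters the primary or relapse results.** The reduction is available only after the Day 14 to 15 EEG, and the SAP efficacy sections do not use the rule; they define relapse by parent report confirmed on video EEG.

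**Conclusion.** The point holds, mainly on SAP 11.3: the rule as written contradicts the protocol's single permitted reduction and the SAP's own dose-change count. The effect is on descriptive exposure and tolerability reporting. The primary test is not affected by this rule. No reliable count of affected infants can be given. About 78 CBD-arm and 24 placebo-arm infants would be in the period where a reduction is possible, if the protocol's response assumptions hold.

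Footnote h is a minor clerical error in an operative table, and misdosing is unlikely. The lag in the SAP reaches further than the exposure tables, because it covers the days of the primary EEG and who enters the extension. It is a version-alignment task, to be finished before database lock. That the SAP is older is an inference from the V2.0 date and the December 2017 citations, since the protocol's version page is not available.

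**What to change.** 1. **SAP 11.3.** Replace the treatment-failure sentence with: *In the Extended Treatment Period a single reduction of CBD or CBD placebo from 40 to 30 mg/kg/day is counted as a dose modification; patients who cannot tolerate 30 mg/kg/day, and withdrawals under protocol 3.3 or 3.5, are counted as discontinued; patients without a Day 14–15 video EEG remain non-responders for EEG endpoints (protocol 8.4.6).* The last clause is needed because SAP 6.4.4 otherwise specifies observed data only, which would leave early intolerance withdrawals without a stated status.

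2. **Footnote h.** Insert *placebo* after the matching 10 mg/kg/day component.

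3. **SAP update to the current protocol.**
   - Regimen: CBD 20/30/40 and vigabatrin 50/100/150 mg/kg/day over 3, 3 and 9 days; extension for Complete Responders only, 75 days; 6-day taper; EEG Day 14 to Day 15. This covers the Technical Summary Report and sections 3.1, 4, 4.2.2 to 4.2.4, 4.3, 6.3.1 (Table 2), 10.3.1 and 11.9.
   - In the same update, remove the partial-to-complete-response endpoints and tests (Technical Summary Report, 9.7, 10.3.2, 10.7.1, 10.7.2). With the extension limited to Complete Responders, they would have no patients.
   - Align the dependent text on study duration, taper eligibility, the CGI-I visit (5.2.2) and laboratory visits (5.3.4).

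The cost is one sentence, one word and an SAP version update. No new data are needed. Removing the two partial-responder hypotheses shortens the SAP 10.3.2 list from eight to six.

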eCRF	electronic case report form
ECG	Electrocardiogram
EDC	electronic data capture
ED ₅₀	median effective dose
EEG	electroencephalogram
EENT	eyes, ears, nose, and throat
FDA	Food and Drug Administration
FSH	Follicle stimulating hormone
GCP	Good Clinical Practice
GLP	Good Laboratory Practice
IB	Investigator's Brochure
ICF	informed consent form
ICD	informed consent document
ICH	International Conference on Harmonisation
IEC	Independent Ethics Committee
INR	international normalized ratio
IP	Investigational product
IRB	Institutional Review Board
IS	Infantile Spasms
ITT	Intent to Treat
IV	Intravenous
LDH	lactate dehydrogenase
LFTs	liver function tests
MCT	Medium Chain Triglycerides
MedDRA	Medical Dictionary for Regulatory Activities
NOAEL	No Observed Adverse Effect Level
OH	Hydroxy
PK	pharmacokinetic(s)
pKa	acid dissociation constant
PT	preferred term
RBC	red blood cell
SAE	serious adverse event

SAP	Statistical Analysis Plan
SD	standard deviation
SOC	System organ class
SOP	standard operating procedure
$t_{1/2}$	terminal phase half-life
TD ₅₀	median tolerated dose
TBL	total bilirubin
TEAE	treatment-emergent adverse event
THC	tetrahydrocannabinol
TLFs	tables, listings, and figures
t_{max}	time to maximum plasma concentration
ULN	upper limit of normal
US	United States

1. INTRODUCTION

Data presented in Section 1.0 include overviews from the nonclinical and clinical published literature that reports on various other formulations of cannabidiol (CBD) (primarily plant-based). Analogous studies have not been completed for Cannabidiol Oral Solution, the pharmaceutical grade synthetic CBD to be investigated in this study.

Please see the Investigator's Brochure (IB)¹ for more information.

1.1. Cannabidiol

The main active constituent of cannabis, Δ^9 -tetrahydrocannabinol (Δ^9 -THC) is the principal psychoactive constituent of marijuana. Cannabidiol is the second most abundant cannabinoid and highly physiologically relevant, but is non-psychoactive. It has demonstrated a potential benefit in treating patients with treatment-resistant epilepsy.^{2,3,4,5}

Insys Development Company, Inc. (hereafter referred to as the Sponsor) has successfully manufactured a pharmaceutical grade, synthetic CBD drug substance. It is manufactured in their current Good Manufacturing Practices (cGMP) manufacturing facility. This facility is approved by the Drug Enforcement Administration (DEA) and has been inspected by the Food and Drug Administration (FDA). This active pharmaceutical ingredient is $\geq 99.5\%$ pure⁶ and can be consistently produced without the concern for contaminant.

1.1.1. Mechanism of Action

The mode of action of CBD is not fully understood. The drug substance manifests a low affinity for endogenous cannabinoid receptors 1 (CB1) and 2 (CB2). Cannabidiol acts as an indirect antagonist of CB1 and inhibits several CB1 mediated Δ^9 -THC effects.⁷ It also stimulates the vanilloid receptor type 1⁸ and modulates the μ - and δ -opioid receptors.⁹ It may also increase plasma Δ^9 -THC levels by inhibiting its hepatic microsomal metabolism by competitively binding proteins in the cytochrome P450 (CYP) oxidative system.¹⁰ Finally, CBD may modulate neuronal hyperexcitability through one or more of the following mechanisms:

- Bidirectional regulation of calcium homeostasis via the mitochondrial sodium/calcium exchanger.¹¹
- Agonistic properties at 5-hydroxytryptamine 1a (5-HT_{1a}) receptors.¹²
- Enhancing endogenous adenosine levels in the central nervous system (CNS) by reducing adenosine re-uptake.^{13,14}

Recent studies have shown that CBD dose-dependently increased seizure threshold in wild-type mice, an effect that was markedly reduced in transient receptor potential vanilloid 1 (TRPV1) channel knockout mice¹⁵, and blocked the G protein-coupled receptor-55 (GPR-55) mediated increase of miniature excitatory postsynaptic currents (mEPSCs) frequency in CA1 pyramidal neurons in healthy and epileptic tissues.¹⁶

